#### **Physical examination:**

A general physical examination should be performed at the time points indicated in the study schedule flowchart [Section 1.2](#). If a new clinically significant abnormality or worsening from baseline is detected after enrollment, then an AE should be reported and the patient should be considered for further clinical investigations and/or specialist consultation as per the Investigator's medical judgment.

### **Blood pressure/heart rate:**

Blood pressure should be measured in sitting position under standardized conditions, approximately at the same time of the day, on the same arm, with the same apparatus if possible (after the patient has rested comfortably in sitting position for at least 5 minutes). The use of calibrated apparatus with age related cuff size is mandatory. Values are to be recorded in the eCRF; both SBP and DBP should be recorded. At the first screening visit, BP should be measured in both arms. The arm with the highest DBP will be determined at this visit, and BP should be measured on this arm throughout the study. This highest value will be recorded in the eCRF.

Heart rate will be measured in sitting position at the time of the measurement of BP.

### **Tanner stages:**

The Tanner stages (18, 19) should be measured by the Investigator at the time points indicated in the study schedule flowchart [Section 1.2](#). Tanner stages are provided in [Appendix C](#). The Tanner stages assessment for each patient at each site should be performed, if possible by the same Investigator/designee trained to assess pubertal development.

### **Body weight and height:**

Body weight should be obtained with the patient wearing undergarments or very light clothing and no shoes, and with an empty bladder. The same scale should be used throughout the study, if possible.

The use of calibrated balance scales is mandatory. Self-reported weights are not acceptable; patients must not read the scales themselves. Height needs to be measured as self-reported heights are not acceptable.

### **Training for new device:**

If a new device is introduced during the course of the study, training will be scheduled accordingly at the next planned visit prior to the first administration.

## **10.1 VISIT SCHEDULE**

The visit schedule and procedures/assessments are listed in the study flow chart in [Section 1.2](#).

The aim of this section is to provide details on how some of the procedures/assessments have to be performed. The study consists of 8 or 9 on-site visits and 1 telephonic visit (follow-up).

If patients are treated with LDL apheresis, the visits from Day 1/Week 0, Week 4 and Week 12 must coincide with an LDL apheresis procedure as well as with study drug administration; study drug will be administered immediately after completion of the LDL apheresis procedure. After Week 12, it is strongly recommended to conduct further visits Week 24 and Week 48 the same day as an LDL apheresis procedure, if these procedures are maintained.

Only patients who meet/are likely to meet the inclusion criteria as noted in [Section 7.1](#) should be screened.

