## 17 APPENDICES

### Appendix A. Management of patients treated with LDL apheresis therapy in the EFC14660 study

#### Introduction

Despite effective available treatments that can also be used in combination, many high-risk patients fail to reach their guideline target LDL-C level. For these patients who are still unable to achieve guideline target level for LDL-C, despite available lipid modifying therapy (LMT), mechanical removal of LDL-C by LDL apheresis is an option.

However, LDL apheresis is a costly procedure that is invasive and burdensome for patients, especially in children. Because of the sparsity of apheresis centers, many patients must travel a significant distance for this procedure, which is administered over 3 hours and must be given every week to every 4 weeks, depending on the patient's LDL-C level and cardiovascular risk. Low-density lipoprotein apheresis is generally well tolerated, but may result in hypotension, hypocalcemia, allergic reactions, and an acute decrease in serum protein levels.

An average reduction of the LDL-C value ranges from 30% to 75% depending on the technique and duration of apheresis (1). With weekly or bi-weekly treatment, the LDL-C levels can be reduced by 40% to 50%. The LDL-C levels rise towards baseline after each apheresis procedure, but do not reach the original levels; with repeated weekly or bi-weekly apheresis, the baseline levels continue to fall until a plateau is reached (2). Alirocumab may offer a significant therapeutic advancement for patients with HoFH who require LDL apheresis by decreasing the frequency or removing the need for apheresis procedures.

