**From Day 1 to Week 12, the apheresis frequency will be fixed to the individual patient's established schedule.**

After Week 12, at the Investigator's discretion, patients may continue to undergo apheresis procedures, as needed and the frequency of apheresis procedures can be adapted to their needs. If these procedures are maintained, it is strongly recommended to conduct the visits Week 24 and Week 48 the same day as an LDL apheresis procedure, in order to collect appropriately the investigational blood samples.

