### **Blood sample collection and overall study assessment throughout the study**

All samples for clinical laboratory (lipid and specialty lipid panels) and PK evaluations **must** be obtained immediately prior to and immediately after the LDL apheresis procedure, therefore LDL apheresis has to be administered at that visit and before study drug administration.

- Lipid panel 1 (Total-C, calculated LDL-C, HDL-C, TG, and non-HDL-C): samples should be drawn immediately prior to and immediately following the apheresis procedure.

---

 Stable apheresis is defined as 4 apheresis procedures performed during a 4 week period, approximately 1 week apart, or 4 apheresis procedures performed during an 8 week period, approximately 2 weeks apart.

*Note: Acceptable apheresis techniques are: double membrane filtration, immunoadsorption, heparin-induced LDL precipitation, direct adsorption of lipids, dextran sulfate adsorption (plasma), dextran sulfate adsorption (whole blood).*

- Alirocumab, and free and total PCSK9 levels: PK samples should be drawn immediately prior to and immediately following the apheresis procedure.
- Specialty lipid panel (lipid panel 2: Apo B, Apo A-1, and Lp (a)): samples should be drawn immediately prior to apheresis (where applicable).
- ADA assessment: samples should be drawn prior to apheresis (where applicable).

Study assessments such as vital signs, BP etc, have to be done before apheresis, and alirocumab is to be administered after apheresis.

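### For patients still on apheresis, the protocol both requires and merely recommends lipid sampling at a procedure at Weeks 24 and 48, so a between-procedure value can be compared with a procedure-day baseline

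*Protocol*

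**What the plan says.** The protocol ties visits to apheresis in three places.

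- **Section 10.1** is strict up to the primary time point: "the visits from Day 1/Week 0, Week 4 and Week 12 must coincide with an LDL apheresis procedure". For later visits it says: "After Week 12, it is strongly recommended to conduct further visits Week 24 and Week 48 the same day as an LDL apheresis procedure", on condition that procedures are maintained.
- **Appendix A, on the course of the study**, repeats the softer rule ("it is strongly recommended to conduct the visits Week 24 and Week 48 the same day as an LDL apheresis procedure") and gives the reason: "in order to collect appropriately the investigational blood samples".
- **Appendix A, on blood sample collection**, has a heading that covers the whole study and is mandatory. For lipid panel 1, "samples should be drawn immediately prior to and immediately following the apheresis procedure"; and "therefore LDL apheresis has to be administered at that visit and before study drug administration".

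The visit lists for Weeks 24 and 48 (Sections 10.1.3.4 and 10.1.3.6) ask for lipid panel 1 before and after apheresis where applicable. Section 9.2.1 makes percent change in LDL-C and the proportion with ≥15% reduction at Weeks 24 and 48 secondary endpoints, on pre-apheresis values where applicable.

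On frequency, the clinical trial summary, Section 10.1.3 and Appendix A all let the investigator adapt apheresis after Week 12. A later paragraph of Section 10.1.3 asks for lipid-modifying therapy, apheresis included, to stay stable during the treatment period except in exceptional circumstances.

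**The concern.** LDL-C in a patient on apheresis follows a cycle. Appendix A describes it: "An average reduction of the LDL-C value ranges from 30% to 75% depending on the technique and duration of apheresis", and then "The LDL-C levels rise towards baseline after each apheresis procedure, but do not reach the original levels". A value has a clear meaning only if its place in the cycle is known. Baseline is fixed just before a procedure. At Weeks 24 and 48 a site can follow Section 10.1 to the letter and draw blood in mid-cycle, when part of the last procedure's effect remains.

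The trial has a single arm, so no control group offsets a shift of this kind. It would pass into the mean percent change and the ≥15% responder count as if it were drug effect. A correctly timed sample cannot be recovered at the analysis stage.

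**Working it through.** The plan states no figure to reproduce here. Section 11.1 says that no sample size calculation was performed; 18 patients are planned.

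**1. The texts side by side**

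| Time point | Section 10.1 and Appendix A (course of the study) | Appendix A (blood sample collection) |
|---|---|---|
| Day 1, Weeks 4 and 12 | mandatory | mandatory |
| Weeks 24 and 48, apheresis maintained | recommended | mandatory |

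The conflict lies between Section 10.1 and Appendix A, and also within Appendix A.

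**2. Illustrative size for one patient**

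Inputs:
- Drug effect d = −0.24. This is an assumption, taken from the figure in Section 4 for another PCSK9 antibody in LDLR-defective patients.
- Drop per procedure R = 0.30 to 0.75 (Appendix A, introduction). Reading that range as the drop per procedure is an assumption.
- Share f of the drop recovered at sampling. This is not in the document and is varied.
- Schedule unchanged since baseline.

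With the pre-procedure baseline set to 1, the pre-procedure value on drug is 1 + d. A between-procedure value is (1 + d)(1 − R(1 − f)). The shift is therefore (1 + d) × R × (1 − f).

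| f | R = 0.30 | R = 0.75 |
|---|---|---|
| 0.25 | 0.76 × 0.30 × 0.75 = 17.1 points | 0.76 × 0.75 × 0.75 = 42.8 points |
| 0.50 | 0.76 × 0.30 × 0.50 = 11.4 points | 0.76 × 0.75 × 0.50 = 28.5 points |
| 0.75 | 0.76 × 0.30 × 0.25 = 5.7 points | 0.76 × 0.75 × 0.25 = 14.3 points |

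At f = 0.50 a true −24% reads −35.4% to −52.5%.

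**3. Effect on a simple mean of 18** (the planned mixed model would differ somewhat)

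- One patient at f = 0.50: 11.4/18 = 0.6 to 28.5/18 = 1.6 points. Over all three values of f: 5.7/18 = 0.3 to 42.75/18 = 2.4 points.
- Three patients (assumed) at f = 0.50: 34.2/18 = 1.9 to 85.5/18 = 4.75 points.

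**4. Responder status with no drug effect (d = 0)**

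The patient counts as a ≥15% responder if R(1 − f) ≥ 0.15, that is f ≤ 1 − 0.15/R. This gives f ≤ 0.50 for R = 0.30 and f ≤ 0.80 for R = 0.75.

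**5. Check of direction with a steady-state cycle model**

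Each procedure removes a share r, and LDL-C returns by first-order rebound at rate k over interval T. Relative to the level without apheresis, the pre-procedure level is P = (1 − e^(−kT))/(1 − (1 − r)e^(−kT)). The level t days after a procedure is 1 − (1 − (1 − r)P)e^(−kt). The reading against a baseline P is (1 + d) × level/P − 1. Inputs are r = 30%, 50% and 75%, T = 7 or 14 days, d = −0.24 and rebound half-lives of 2, 3 and 5 days. The half-lives are assumed.

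- Unchanged schedule, sample just before a procedure: −24.0% in every scenario.
- Unchanged schedule, mid-interval: −26% to −46%, an overstatement of about 2 to 22 points.
- Unchanged schedule, a quarter of the way through: −31% to −61%.
- Frequency halved: just before a procedure −24% to −2%; mid-interval −24% to −21%.
- Apheresis stopped: −24% to +11%.

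**6. Can the visit be planned on a procedure day?**

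Procedures coincide with Day 1 and Weeks 4 and 12. A weekly or 2-weekly schedule kept from there also falls on Weeks 24 and 48. If the schedule has drifted but is regular, the Week 24 window (±7 days, 15 days) always contains a weekly or 2-weekly procedure. The Week 48 window (±3 days, 7 days) always contains a weekly one, but a 2-weekly one for only 7 of 14 possible timings and a 4-weekly one for 7 of 28.

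**The case against.** The strongest reply is that the plan already asks for the right value. The percent-change and responder endpoints specify pre-apheresis LDL-C, and the Week 24 and 48 visit lists order samples before and after apheresis. The protocol nowhere says that a mid-cycle value counts as pre-apheresis. Whether to use, flag or discard such a value is normally for the SAP, which is not at hand. That stands as a limit on the consequence, since overstatement needs the value to be accepted as pre-apheresis. It does not remove the problem. Neither rule in Section 9 gives a timing relative to the next procedure, and if the value is discarded, an observation is lost in a very small trial.

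A reader might infer that Week 24 and 48 results in apheresis patients are biased in favour of the drug in general. The documents do not support that. Appendix A hopes that alirocumab will make apheresis less frequent or unnecessary. In the modelled cases of halved or stopped apheresis, the reading was about right or understated. That follows from a permitted schedule change, which is a deliberate choice and not an effect of this conflict.

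It may also be said that the mandatory rule would force a procedure on a patient who has stopped. Read literally it could, but the preceding paragraph of Appendix A is conditional on procedures being maintained, so this is a matter of tidying the scope.

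The stability sentence in Section 10.1.3 conflicts with the permission to adapt frequency. That permission is specific and appears three times, so this too is only a wording correction.

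**Conclusion.** The sampling conflict is real and minor. For a patient still on apheresis after Week 12, one rule requires a procedure-day sample and two others only recommend it, so a mid-cycle sample at Week 24 or 48 is open to a compliant site. On an unchanged or denser schedule, and if the value is used as pre-apheresis, that patient's LDL-C reduction is overstated and responder status may be wrongly credited.

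The size cannot be fixed from the document. The per-patient figures rest on an assumed rebound, a drug effect borrowed from another antibody, and a reading of the 30% to 75% range as the drop per procedure. The effect on the cohort also depends on an unknown number of apheresis patients. The direction is secure only under the two stated conditions.

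Patients not on apheresis are unaffected. The Week 12 primary is protected by the fixed apheresis schedule and the mandatory procedure-day visits, so nothing here bears on the primary result.

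**What to change.** 1. In Section 10.1 and the matching paragraph of Appendix A, require that patients still on apheresis have the Week 24 and Week 48 lipid samples drawn immediately before a procedure, planned into the visit window. A maintained weekly or 2-weekly schedule does this without extra procedures.
2. Limit the mandatory sampling rule in Appendix A to patients still on apheresis.
3. Record the date of the last procedure and the current interval. The flow chart already checks apheresis frequency through Week 48, so part of this is in place. The interval matters because a pre-procedure sample after a longer interval than at baseline carries more rebound.
4. Flag any sample drawn outside the window or between procedures, and do not treat a between-procedure value as pre-apheresis.
5. If a Week 48 sample has to move to the nearest procedure, set Week 49 as the limit and flag it. The last injection is at Week 46 and the on-treatment period ends 21 days later. Such a sample can fall 3 weeks after the last injection where 2 are planned, which exchanges part of an apheresis-cycle mismatch for a dosing-cycle one.
6. As a wording correction, limit the mention of apheresis in the stability sentence of Section 10.1.3 to the period up to Week 12.

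The cost is a wording amendment and two case report form fields. A few visits must be rescheduled, and a few values may be flagged or fall at a different point of the dosing cycle. None of this removes the effect of permitted schedule changes, which should be acknowledged when the Week 24 and 48 results are interpreted.

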### **10.1.1 Run-in period (as needed, up to Week -6)**

Patients who consent to participate in the study, but who have not been on stable LMTs for at least 4 weeks or require statin intensification when initially seen, can participate in a run-in period until LMT dose(s) have been stable for at least 4 weeks. Patients eligible for the run-in period are expected to fulfill the LDL-C eligibility criterion at the end of the run-in period. Patients who require treatment with statin de novo are not allowed to enter the run-in period in order to avoid the potential for multiple titration steps. Patients who have initiated apheresis procedure (every week or every other week) at least 6 months prior to giving informed consent to the study, can enter the run-in period.

Another possible situation requiring the run-in period includes patients with suspected hoFH based on clinical criteria but without confirmation by previous genetic testing. Such patients will be asked to undergo centralized genotyping testing during the run-in period.

The run-in period is up to 4 weeks (+2 days) in duration, with 1 visit.

Patients can enter the screening period as soon as the criterion for stable LMT is met and/or centralized genotyping data (if no previous genotyping) are available.

#### **10.1.1.1 Visit 1 (Week -6, Run-in)**

- Obtaining the informed consent:
  - The patient will receive verbal information concerning the aims and methods of the study, its constraints and risks, and the study duration. Written information will be provided to the patient. Written informed consent must be signed by the patient and Investigator prior to any investigations.
- Obtaining the hoFH Genotyping Informed Consent from the dedicated section in the main ICF (if needed, ie, if no previous result of genotyping is available).
- Assessment of inclusion/exclusion criteria.
- Collection of demographic data (age, gender, race, and ethnic origin).
- Medical/surgical/family medical history.
- Record habits: alcohol habits (during the last 12 months), smoking status.
- Document prior medication history within the previous 12 weeks, especially for LMT (including statin) and nutraceutical products that may affect lipids (eg, omega-3 fatty acids, plant stanols such as those found in Benecol, flax seed oil, and psyllium).
- Check of stability of background LMT, including apheresis schedule (see [Appendix A](#)).
- Review of diet.
- Physical examination including vital signs (heart rate, SBP and DBP in sitting position) in both arms.
- Body weight measurement.

- Height without shoes.
- Tanner stage.
- Collect AEs from this point onward:
  - All AEs and SAEs will be collected from the time of informed consent signature and throughout the study.
- Sampling for hoFH genotyping (if needed).
- IRT will be contacted for notification of screening and for patient number allocation.

### **10.1.2 Screening period**

For all patients regardless of their participation in a run-in period, the screening period is up to 2 weeks (+5 days) in duration.

The injection training will occur during the screening period after the eligibility criteria have been checked and it is confirmed that the patient is likely to be included. Patients aged  $\geq 12$  years (or another designated person such as parent, etc) will be trained to self-inject/inject with placebo for alirocumab. Patients 8 to 11 years old will be assigned a parent or another designated person who will be trained during the injection training visit or an alternative arrangement. In all cases, alternative arrangements for this required injection training may be allowed as needed, regardless of age. Please note that this visit (injection training visit) can take place at the same visit as D1 as per the site or patient preference. Prior to the injection, a local topical anesthetic may be utilized as per the Investigator's judgment. Investigators will have the option of providing a second placebo kit for alirocumab for patients/parents who require additional injection training prior to enrollment.

All laboratory tests measured at the central laboratory needed for checking the exclusion criteria of the patients will be performed during the screening period.

The screening period may include more than one site visit for patients for whom not all screening procedures can be done at the first visit. The sample for lipid testing must be obtained only after the patient has been on a stable LMT therapy (optimal statin dose  $\pm$  other LMT, including apheresis) for at least 4 weeks.

Patients can be enrolled after the injection training visit and as soon as all inclusion and no exclusion criteria are met.

Patients will be instructed to follow a diet to treat their hypercholesterolemia in accordance with local guidelines or treatment practice and they should be on this diet throughout the entire study duration.

#### **10.1.2.1 Visit 2 (Up to Week -2, Screening visit)**

For the complete list and contents of procedures/assessments scheduled for the screening period, please refer to the Study Flow Chart in [Section 1.2](#) and for detailed description of assessments [Section 9](#) and [Section 10.6](#).

The following procedures/assessments will be performed at the Screening visit:

- Obtaining the informed consent (if the patient did not have a run-in period):
  - The patient will receive verbal information concerning the aims and methods of the study, its constraints and risks and the study duration. Written information will be provided to the patient. Written informed consent must be signed by the patient and Investigator prior to any investigations.
- IRT will be notified (allocation of patient number, registration of screening, collection of demographic information). The patient number is composed of a 12-digit number containing the 3-digit country code, the 4-digit center code and the 5-digit patient chronological number (which is 00001 for the first patient screened in a center, 00002 for the second patient screened in the same center, etc).
- Assessment of inclusion/exclusion criteria.
- Check of stability of background LMT, including apheresis schedule (if applicable)
- If not collected before:
  - Collection of demographic data (age, gender, race, and ethnic origin).
  - Collection of genotyping results.
  - Medical/surgical/family medical history.
  - Record habits: alcohol habits (during the last 12 months), smoking status.
  - Document prior medication history within the previous 12 weeks, especially for LMT (including statin) and nutraceutical products that may affect lipids (eg, omega-3 fatty acids, plant stanols such as those found in Benecol, flax seed oil, and psyllium).
  - Review of diet.
  - Physical examination including vital signs (heart rate, SBP and DBP in sitting position) in both arms.
  - Body weight measurement.
  - Height without shoes.
  - Tanner stage.
- Collect AEs.
- Fasting blood sampling for:
  - Total-C, LDL-C, HDL-C, TG, and non-HDL-C (pre-apheresis and post-apheresis, if applicable).
  - Hematology and chemistry.
  - HbA1c.
  - CPK.
  - Liver panel.
  - Pregnancy test.

